2.5.3.5 Prohibited Medications

Sirolimus is prohibited from use from the time of enrollment through completion of study drug.

Treatment with any other investigational product is not allowed while on study treatment. An investigational product is defined as medications without any known FDA or EMA approved indications.

2.5.4 Follow-Up Post Treatment Discontinuation

Participants may withdraw from treatment at any time for any reason. The reason should be documented by the study team. However, participants that have received at least one treatment dose are evaluable for all endpoints of the study and should continue with protocol-specific follow-up and data collection unless consent to study is withdrawn. Enrolled participants that do not receive any study treatment may be replaced. Participants that receive at least one treatment dose remain on study and are evaluable for all endpoints as above.

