5 STATISTICAL CONSIDERATIONS

5.1 STUDY DESIGN AND OBJECTIVE

This trial is a randomized, open-label, multi-center Phase 3 study designed to compare the efficacy and safety of T-Guard to ruxolitinib treatment of participants with Grade III-IV SR-aGVHD. A total of 246 participants will be enrolled from approximately 75 transplant centers in the US and Europe. All participants will be followed at minimum through Day 180 post-randomization.

The study will begin with a safety run-in phase of 24 randomized participants (12 to each arm), after which the remaining participants will be enrolled provided that safety concerns do not arise during the run-in.

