5.1.2 Randomization and Blinding

Participants will be randomized at the time of enrollment in a 1:1 ratio to the treatment arms. Randomization will be stratified by center region (US vs. Europe) and age group (at least 55 years vs. under 55). Stratified treatment assignments will be generated using permuted blocks of random sizes.

As this is an open-label trial, no blinding will be performed.

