5.1.3 Analysis Populations

The primary analysis population will include all randomized participants classified according to the intention-to-treat (ITT) principle, that is, according to their randomized assignment.

A secondary, supportive analysis of a per protocol (PP) population will be performed. The PP population will consist of all participants from the ITT population who received at least one dose of the assigned treatment.

A PK analysis population will be defined for the assessment of pharmacokinetic and immunogenicity endpoints in the T-Guard arm only. This will consist of the participants randomized to T-Guard from whom samples have been collected and evaluated for these endpoints.

Note that because the safety run-in phase is randomized, the inclusion of its participants in the analysis will not contribute bias. Therefore, run-in participants will be included in the ITT population and in the PP and PK populations as long as the other requirements for inclusion are satisfied.

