5.5 ANALYSIS OF PRIMARY ENDPOINT

The primary endpoint of this trial is the attainment of a CR at Day 28 post-randomization. The primary hypothesis is that the proportion of participants with a CR at Day 28, called the Day 28 CR rate, is greater for the T-Guard arm compared to the ruxolitinib arm. This hypothesis will be evaluated by comparing the null hypothesis that the Day 28 CR rate under T-Guard treatment is no better than this rate under ruxolitinib treatment to the alternative hypothesis that this rate is superior for the T-Guard arm.

The estimand for Day 28 CR is based on the composite strategy, where a participant is classified as a CR provided three conditions are satisfied:

1. Stage 0 aGVHD in target organs at Day 28
2. The participant is still alive at Day 28
3. No additional systemic treatment for aGVHD has been administered through Day 28

Participants who do not satisfy all three criteria will be classified as failures for CR.

The following intercurrent events could potentially impact the pivotal analysis: discontinuation of study drug before Day 28, and missingness of the Day 28 GVHD assessment. The pivotal analysis accounts for these events as follows:

- Discontinuation of study drug will be carefully monitored. Under the ITT principle, the analysis includes all randomized participants, so treatment discontinuation itself has no effect on the analysis because it produces no changes to the participant population or evaluation of CR criteria. Initiation of additional systemic aGVHD treatment following discontinuation would be considered a failure for CR per the composite strategy described above.
- Participants whose Day 28 GVHD assessment is missing for any reason (including loss to follow-up, withdrawal from study, or a missed visit) will be classified as failures (non-CRs) for the primary endpoint.

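### Section 2.5.4 lets randomized participants who never start treatment be replaced, and promises follow-up only to dosed participants, in conflict with the all-randomized analysis and the 180-day follow-up of everyone

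*Combined protocol and SAP*

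**What the plan says.** Section 2.5.4 states that "participants that have received at least one treatment dose are evaluable for all endpoints of the study and should continue with protocol-specific follow-up", subject to consent, and repeats that such participants stay on study. About participants who took no dose it says only this: "Enrolled participants that do not receive any study treatment may be replaced".

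Section 5.1.2 makes enrollment the moment of randomization: "Participants will be randomized at the time of enrollment in a 1:1 ratio to the treatment arms". Section 4.2 describes the same single step in the data system.

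Chapter 5 covers everyone randomized. On follow-up, section 5.1 says "All participants will be followed at minimum through Day 180 post-randomization", and the synopsis also gives 180 days from randomization. On the analysis set, section 5.1.3 says "The primary analysis population will include all randomized participants classified according to the intention-to-treat (ITT) principle". The per-protocol definition there confirms that undosed participants belong to ITT: "The PP population will consist of all participants from the ITT population who received at least one dose of the assigned treatment".

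Section 5.5 sets three conditions for CR: stage 0 in the target organs, alive, and no additional systemic aGVHD treatment through Day 28. Having received the assigned drug is not among them. "Participants who do not satisfy all three criteria will be classified as failures for CR", and so are "Participants whose Day 28 GVHD assessment is missing for any reason".

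**The concern.** The two parts of the document give a site different instructions for a randomized participant who never starts. Under chapter 5 the person is followed and analyzed. Under section 2.5.4 the person may be replaced, and nothing in that section asks for further visits. It is the section a site would consult in this situation.

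Three questions have no answer anywhere: whether a replaced participant stays in the ITT set, whether the replacement counts within or above the 246, and how it is allocated under stratified permuted blocks. Section 5.5 names two intercurrent events, discontinuation and a missing Day 28 assessment. Never starting is not one of them. Section 5.2.1 does have a rule for non-starters, but only in a secondary FDA analysis and only for T-Guard.

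At stake are the Day 28 status of non-starters, which becomes failure if it is not collected, and their survival data for OS, the alpha-protected key secondary endpoint. Non-starting could differ by arm. The trial is open-label, inpatient dosing is strongly recommended for T-Guard (2.5.1.4), ruxolitinib is an oral drug with its own conditions for delaying the start (2.5.2.4), and up to 72 hours may pass between randomization and first dose (2.5).

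**Working it through.** **Inputs.** CR rates 43% and 26%, one-sided 2.5%, 246 participants (5.1.5). Looks at 150 and 246 participants with Z boundaries 2.6562 and 1.9817 (Table 5-2). Futility at 4 or fewer CRs in 23 T-Guard participants (Table 5-1). Non-start rates are assumptions. The only figures in the documents are those of REACH2 (1.3.2.1): 152 of 154 and 150 of 155 were treated, so 2/154 = 1.3% and 5/155 = 3.2% were not.

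**Plan's figures reproduced.** For a fixed design, n per arm = [1.960·√(2·0.345·0.655) + 0.842·√(0.43·0.57 + 0.26·0.74)]² / 0.17² = (1.318 + 0.557)² / 0.0289, about 122. That is 244 in total, against 246 stated. The binomial probability of 4 or fewer CRs in 23 is 50.1%, 24.8% and 0.9% at true rates of 20%, 26% and 43%, as in Table 5-1. The full two-look design, with an unadjusted pooled Z test and exact binomial probabilities, gives 79.9% power (stated 80.56%) and 2.3% type I error (stated 2.37%).

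**Dilution.** If a fraction w of an arm never starts and all of them are scored as failures, the observed CR rate is p·(1 − w). For example, T-Guard at w = 3.2% gives 0.43 × 0.968 = 0.416, and ruxolitinib at w = 1.3% gives 0.26 × 0.987 = 0.257. Power uses 43% vs 26% among those treated. Type I error uses 26% in both arms.

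| Assumed non-start (T-Guard / ruxolitinib) | Result at N = 246 |
|---|---|
| none | power 79.9%, type I error 2.3% |
| 1.3% / 1.3% | power 79.1% |
| 3.2% / 3.2% | power 77.8% |
| 3.2% / 1.3% | power 75.1% |
| 1.3% / 3.2% | type I error 2.8% |
| 5% / 5% | power 76.5% |
| 5% / 0% | power 69.0% |
| 0% / 5% | type I error 3.9% |

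In persons, 1.3% and 3.2% of 123 are about 2 and 4 per arm, and 5% is about 6.

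**What the table leaves out.** It scores every non-starter as a failure. Some would be failures even with full follow-up, because they receive other systemic aGVHD therapy, die, or are above stage 0. The gap to the first row is therefore an upper bound on what better follow-up recovers. Covariate adjustment, which section 5.1.5 expects to add power, is not modelled.

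**The case against.** A reader might infer from section 2.5.4 that non-starters need not be followed. The documents do not settle that. Section 5.1 and the synopsis follow all participants, section 4.3.1 times visits from randomization, and it also requires registry (CIBMTR) forms to continue for everyone enrolled. Section 2.5.4 never tells a site to stop. What stands is a conflict between sections.

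A reader might also infer that replacement by itself breaks ITT. It does not, because adding a participant removes no one. The ITT analysis is broken only if the replaced person is dropped, and the text leaves that open. Replacement may be meant to fill the FDA population of treated T-Guard participants (5.2.1), though the text does not say so.

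Nor are non-starters automatic failures. One who is assessed at Day 28 as stage 0, alive and without additional systemic therapy is a CR under section 5.5. Failure is certain only when the assessment is missing or another condition fails. Likewise, no section says that non-starters are censored for OS at withdrawal; loss of their survival data is a risk, not a written rule.

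Finally, the 5% one-arm rates have no source in the documents, and the 72-hour limit (ideally 24 hours, section 4.2.1) should keep non-starting rare. That is a fair limit on the size. It does not remove the conflict.

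**Conclusion.** The point holds as an internal inconsistency with a practical consequence. Section 2.5.4 must be reconciled with sections 5.1, 5.1.3 and 5.5, because a site that relies on it alone can lose Day 28 and survival data for randomized participants, and those data cannot be recovered later.

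At the REACH2 non-start rates the effect is modest: a loss of about 1 to 2 points of power if the arms are alike, about 5 points if T-Guard has the higher rate, and a type I error of 2.8% against the 2.5% limit if ruxolitinib does. An assumed 5% in one arm only would matter much more (69.0% power, or 3.9% type I error). All of these figures rest on assumed rates and on every non-starter counting as a failure.

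**What to change.** In section 2.5.4, state that every randomized participant, dosed or not, stays in the ITT set and has the Day 28 aGVHD assessment, recording of systemic aGVHD therapy, and survival follow-up through Day 180, unless consent is withdrawn.

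Then either delete the replacement sentence, or state that any added participant (for example, to fill the treated FDA cohort of section 5.2.1) is extra to the 246 and does not displace the untreated participant.

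The cost is a few sentences of protocol text and follow-up of a small number of untreated participants. The planned sample size does not change unless the sponsor chooses to add participants.

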2.6 STUDY CONDUCT

This study will be conducted in accordance with the protocol, the BMT CTN 2002 protocol-specific Manual of Procedures (MOP), and the following:

- Consensus ethical principles derived from international guidelines including the Declaration of Helsinki
- Applicable ICH Good Clinical Practice (GCP) Guidelines
- Applicable laws and regulations

The National Marrow Donor Program (NMDP) single Institutional Review Board (IRB) of Record will oversee this study and conduct the study-specific reviews as required by federal regulations and per the NMDP IRB Standard Operating Procedures (SOPs) for centers in the United States. For centers within Europe, the oversight and conduct of the study-specific reviews will be based on the country-specific regulations.

Site personnel will enter data in the electronic case report form (eCRF) in the electronic data capture system (EDC) as described in the BMT CTN 2002 eCRF Completion Guide. Source documentation should be made available for monitoring visits, audits and regulatory inspections as described in the BMT CTN 2002 protocol-specific MOP.

Participating PIs bear ultimate responsibility for training of site staff as well as the scientific, technical, and administrative aspects of conduct of the protocol, even when certain tasks have been delegated to sub-investigators or staff. The PIs have a responsibility to protect the rights and welfare of participants and comply with all requirements regarding the clinical obligations and all other pertinent requirements in 21 CFR part 312 and ICH GCP. In addition to following applicable federal, state, and local regulations, investigators are expected to follow ethical principles and standards and receive training in GCP every three years and human subjects training within the past 3 years and thereafter as per institutional requirements.

2.7 STUDY TERMINATION

Regulatory agencies have the right to terminate the study at any time in case of safety concerns or if special circumstances concerning the study drug or the company itself occur, making further treatment of participants impossible. The study sponsor also has the right to terminate the study. In this event, the Investigator(s) and relevant authorities will be informed of the reason for study termination.

CHAPTER 3

3 STUDY ENDPOINTS

3.1 ACUTE GVHD RESPONSE DEFINITIONS

Scoring of aGVHD response on a given day is in comparison to the participant's aGVHD staging on the day of randomization. Organ staging will be assessed using the MAGIC criteria (see APPENDIX C) and response will be scored as defined below:

Complete response (CR) is defined as a score of 0 for the GVHD staging in all evaluable organs. For example, for a response to be scored as CR, the participant must still be in CR on that day and have had no intervening additional systemic therapy for treatment of aGVHD.

Partial response (PR) is defined as improvement in one or more organs involved with GVHD symptoms without progression in others. For example, for a response to be scored as PR, the participant must still be in PR on that day and have had no intervening additional systemic therapy for treatment of aGVHD.

Mixed response (MR) is defined as improvement in one or more organs with deterioration in another organ manifesting symptoms of GVHD or development of symptoms of GVHD in a new organ.

No response (NR) is defined as absence of any improvement or progression as defined. Participants receiving additional systemic therapy will be classified as non-responders.

Progression is defined as deterioration in at least one organ without any improvement in others.

Loss of CR is defined as progression of aGVHD symptoms requiring additional systemic therapy (including escalation of corticosteroid dose to or beyond 2mg/kg methylprednisolone (or equivalent)); death; or if the participant develops new target organ symptoms that could qualify as being from either aGVHD or cGVHD (if the new symptoms are only associated with cGVHD then this is not considered a loss of CR).

3.2 RELAPSE DEFINITION

Malignancy relapse is defined as follows:

Relapse is defined by either morphological or cytogenetic evidence of acute leukemia or MDS consistent with pre-transplant features, or radiologic evidence of lymphoma, documented or not by biopsy. Progression of disease applies to participants with lymphoproliferative diseases (lymphoma or chronic lymphocytic leukemia) not in remission prior to transplantation. The event is defined as increase in size of prior sites of disease or evidence of new sites of disease, documented or not by biopsy.

Acute leukemia, CML and MDS – Relapse will be diagnosed when there is:

- Reappearance of leukemia blast cells in the peripheral blood; or,
- Greater than 5% blasts in the bone marrow, not attributable to another cause (e.g., bone marrow regeneration)
- The appearance of previous or new dysplastic changes (MDS specific) within the bone

marrow with or without falling donor chimerism; or

- The development of extramedullary leukemia or leukemic cells in the cerebral spinal fluid or
- The reappearance of cytogenetic abnormalities present prior to transplantation

Lymphoproliferative Diseases – Relapse or progression will be diagnosed when there is:

- Appearance of any new lesion more than 1.5 cm in any axis during or at the end of therapy, even if other lesions are decreasing in size. Increased fluoro- deoxyglucose (FDG) uptake in a previously unaffected site will only be considered relapsed or progressive disease (PD) after confirmation with other modalities. In participants with no prior history of pulmonary lymphoma, new lung nodules identified by CT are mostly benign. Thus, a therapeutic decision should not be made solely on the basis of the positron emission tomography (PET) without histologic confirmation.
- At least a 50% increase from nadir in the sum of the product diameters of any previously involved nodes, or in a single involved node, or the size of other lesions (e.g., splenic or hepatic nodules). To be considered PD, a lymph node with a diameter of the short axis of less than 1.0 cm must increase by $\geq 50\%$ and to a size of 1.5 x 1.5 cm or more than 1.5 cm in the long axis.
- Lesions should be PET positive if observed in a typical FDG-avid lymphoma or the lesion was PET positive before therapy unless the lesion is too small to be detected with current PET systems (less than 1.5 cm in its long axis by CT).
- In addition to the criteria above, participants with chronic lymphocytic leukemia (CLL) who present in complete remission prior to transplantation may fulfill the relapse definition if there is reappearance of circulating malignant cells that are phenotypically characteristic of CLL.

Multiple Myeloma – Clinical relapse is defined as meeting one or more of the following criteria:

- Direct indicators of increasing disease and/or end organ dysfunction (CRAB features) related to the underlying clonal plasma-cell proliferative disorder. It is not used in calculation of time to progression or progression-free survival but is listed as something that can be reported optionally or for use in clinical practice;
- Development of new soft tissue plasmacytomas or bone lesions (osteoporotic fractures do not constitute progression);
- Definite increase in the size of existing plasmacytomas or bone lesions. A definite increase is defined as a 50% (and greater than or equal to 1 cm) increase as measured serially by the SPD^{§§} of the measurable lesion;
- Hypercalcemia (greater than 11 mg/dL);
- Decrease in hemoglobin of greater than or equal to 2 g/dL not related to therapy or other non-myeloma-related conditions;
- Rise in serum creatinine by 2 mg/dL or more from the start of the therapy and attributable to myeloma;
- Hyper viscosity related to serum paraprotein.

For the purposes of assessing relapse free survival (RFS), if the participant is in a CR, any one or more of the following will be considered a relapse:

- Reappearance of serum or urine M-protein by immunofixation or electrophoresis;
- Development of greater than or equal to 5% plasma cells in the bone marrow;
- Appearance of any other sign of progression (i.e., new plasmacytoma, lytic bone lesion, or hypercalcemia see above).

Myeloproliferative Neoplasms: Relapse from CR is defined as:

- Reappearance of bone marrow disease, including blasts, monocytic blast equivalents, or fibrosis
- New extramedullary disease, including new or reappearance of splenomegaly, hepatomegaly, skin lesions, etc.

***Institution of any therapy to treat persistent, progressive or relapsed malignancy, including the withdrawal of immunosuppressive therapy or treatment of relapse with donor lymphocyte infusion, will be considered evidence of relapse/progression regardless of whether the criteria described above were met. The use of preemptive donor lymphocyte infusion is not considered as relapse.**

Non-malignant Diseases: Non-malignant diseases will be considered to have a transplant status of persistent/active disease. Graft failures will be considered recurrence.

3.3 PRIMARY ENDPOINT

The primary endpoint is the proportion of participants with a CR on Day 28 after randomization.

3.4 SECONDARY ENDPOINTS

3.4.1 Key Secondary Endpoints:

3.4.1.1 Overall Survival (OS)

OS will be assessed at Days 60, 90 and 180 post-randomization. An event for this analysis is death from any cause and time will be calculated from randomization until date of death.

3.4.1.2 Duration of Complete Response (DoCR)

DoCR is defined as the time from Day 28 until an aGVHD target organ worsens by at least 1 stage and requires a significant escalation in treatment (defined below), or death. The transient worsening of symptoms that resolve without significant escalation of treatment is not considered a loss of CR. A significant escalation in treatment is defined as initiation of new systemic treatment for GVHD and/or escalation in methylprednisolone dose (or equivalent).

Methylprednisolone dose increases must be greater than 25% of the current dose and increase at least 8 mg/day (or other steroid equivalent) to be considered an escalation of methylprednisolone. DoCR will be evaluated in the set of participants who are in CR on Day 28 after randomization.

3.4.2 Other Secondary Endpoints:

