2.5.1.7 T-Guard Discontinuation

T-Guard treatment must be completed within 14 days of the first study drug dose. Participants who have missed doses may re-start T-Guard provided it is within the 14-day treatment window.

2.5.1.8 aGVHD Progression or Non-response

If additional systemic aGVHD treatment, other than steroids, is added for lack of response or progression, T-Guard treatment must be discontinued and not re-instituted.

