2.5.2.3 Dose and Administration of Ruxolitinib

Participants randomized to the ruxolitinib arm will receive 10mg orally twice daily to begin on Day 0. Dose modifications for toxicity are described below. Participants responding to treatment may be tapered off ruxolitinib as needed, starting no earlier than Day 56. The dose tapering strategy should be based on evaluation of the condition of the participant, current dosing regimen and the clinical judgment of the Investigator.

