Participants who have had a dose reduction of ruxolitinib in order to manage toxicity may resume treatment at the previous dose as noted in Table 2-2 if hematologic/non-hematologic parameters meet the required threshold(s) at patient eligibility. Dose re-escalation levels of ruxolitinib are described in [Table 2-3](#). Dose increases may not exceed 10 mg BID, with increments of 5mg twice daily and not more often than every 2 weeks.

Table 2-3: Dose Re-escalation for ruxolitinib

Current Dose	First Dose Escalation	Second Dose Escalation
5 mg once daily	5 mg twice daily	10 mg twice daily
5 mg twice daily	10 mg twice daily	-

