2.5.3.4 Salvage Treatment Guidelines

Addition of any new systemic immunosuppressive therapy by the Investigator after the start of T-Guard or ruxolitinib treatment is allowed:

- After 7 days for participants meeting aGvHD criteria for progression or mixed response
- After 14 days for participants meeting aGVHD criteria for no response

In case T-Guard infusions are delayed (e.g., for toxicity reasons) the day 7 and 14 timepoints will shift accordingly.

Requirement for initiation of new systemic immunosuppressive therapy will be considered a treatment failure. In this case, the participant must discontinue study treatment.

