5.6.2 Duration of Complete Response (DoCR)

DoCR will be evaluated only in the set of participants who are in CR at Day 28 post-randomization. The primary definition of DoCR is the time from Day 28 until an aGVHD target organ worsens by at least 1 stage and requires a significant escalation in treatment (defined below), or death. The transient worsening of symptoms that resolve without significant escalation of treatment is not considered a loss of CR. A significant escalation in treatment is defined as initiation of new systemic treatment for GVHD and/or escalation in methylprednisolone dose (or equivalent). Methylprednisolone dose increases must be greater than 25% of the current dose and increase at least 8 mg/day (or other steroid equivalent) to be considered an escalation of methylprednisolone. DoCR will be described for each arm using the Kaplan-Meier estimator, with estimates and 95% CIs for the median of DoCR obtained from this estimator using the method described in Andersen et al. 1993, Chapter IV.

A Cox proportional hazards model will compare the hazard rates of loss of CR between the T-Guard and ruxolitinib arms through Day 180 while adjusting for the stratification factors. This will include DoCR events as defined in the previous paragraph.

A secondary analysis will use an alternative definition of DoCR as the time from Day 28 until death or a significant escalation of aGVHD therapy occurs, as defined in the primary analysis of DoCR. DoCR defined in this manner will be described for each arm using the Kaplan-Meier estimator, with estimates and 95% CIs for the median of DoCR obtained from this estimator using the method described in Andersen et al. 1993, Chapter IV.

Other Secondary Endpoints:

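### Raising ruxolitinib for a flare is not a DoCR event in the ruxolitinib arm, but giving ruxolitinib for the same flare after T-Guard is

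*Combined protocol and SAP*

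**What the plan says.** Section 3.4.1.2 sets the event: "DoCR is defined as the time from Day 28 until an aGVHD target organ worsens by at least 1 stage and requires a significant escalation". Death also ends the duration. The section then defines escalation: "A significant escalation in treatment is defined as initiation of new systemic treatment for GVHD and/or escalation in methylprednisolone dose (or equivalent". A steroid increase qualifies only if it exceeds 25% of the current dose and is at least 8 mg/day. Section 5.6.2 repeats this and adds: "The transient worsening of symptoms that resolve without significant escalation of treatment is not considered a loss of CR". The comparison is a Cox model through Day 180. The alternative DoCR definition in 5.6.2 drops the organ-worsening condition but keeps the same meaning of escalation.

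The two study drugs behave differently over the Day 28 to Day 180 window. Section 2.5.1.7: "T-Guard treatment must be completed within 14 days of the first study drug dose". Section 2.5.2.3: "Participants responding to treatment may be tapered off ruxolitinib as needed, starting no earlier than Day 56", with the taper strategy left to the investigator's judgment. Section 2.5.2.5 allows ruxolitinib to go back up ("Dose increases may not exceed 10 mg BID, with increments of 5mg twice daily and not more often than every 2 weeks"), but that text concerns participants whose dose was reduced for toxicity.

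Section 5.6 names overall survival and DoCR as the key secondary endpoints and alpha-protects only overall survival.

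**The concern.** A stage-worsening flare counts only through one of two treatment changes, and a ruxolitinib dose increase is not one of them. In the T-Guard arm the study drug is finished well before Day 28, so ruxolitinib given for a flare is a new systemic treatment and the flare is an event. In the ruxolitinib arm the assigned drug is still adjustable. A flare managed only by more of it leaves no event, although the organ change and the rescue drug are the same.

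What counts as an event then depends on the arm. Durability after a short T-Guard course, compared with continuing ruxolitinib, is what DoCR is meant to describe, and the estimate would be tilted toward ruxolitinib. Neither planned DoCR analysis would show it, because both use the same escalation rule.

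**Working it through.** The plan gives no event count, hazard ratio or power for DoCR, so there is no figure of its own to reproduce. The check has two parts.

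**1. The wording, applied to the same flare (one organ worse by at least one stage, after Day 28).**

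| Management | T-Guard arm | Ruxolitinib arm |
|---|---|---|
| Qualifying steroid increase | Event | Event |
| Another systemic agent added | Event | Event |
| Ruxolitinib started | Event (new treatment) | Not applicable |
| Assigned ruxolitinib raised, nothing else | Not applicable | No event |
| Ruxolitinib restarted after a full stop | Not applicable | Not stated |

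Reading new treatment as excluding the assigned drug is supported by section 2.5.3.4. It says "Addition of any new systemic immunosuppressive therapy by the Investigator after the start of T-Guard or ruxolitinib treatment is allowed" under certain conditions, and then requires study treatment to be discontinued. That would make no sense if the new therapy were the study drug itself.

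The ruxolitinib taper is open from Day 56, that is for 180 − 56 = 124 of the 180 − 28 = 152 days in the window. Before Day 56, with a 10 mg twice-daily starting dose and ceiling, only participants whose dose had been reduced or held could have an increase.

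**2. Possible size.** Inputs:
- 123 participants per arm (246 randomized 1:1) and a Day 28 CR rate of 26% for ruxolitinib (section 5.1.5). Responders: 123 × 0.26 = 32.
- Loss of response by 6 months of 10% with ruxolitinib and 39% with control in the earlier randomized trial (section 1.2.3). These are losses of overall response in a population not limited to Grade III-IV, so they serve only as a range.
- The share h of ruxolitinib-arm flare events managed by raising ruxolitinib alone. The documents give no figure; 10%, 20% and 30% are assumed.
- The share d of DoCR events that are deaths. The documents give none; 0 and one half are shown.

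Hidden events = 32 × loss × h, taking every loss as a flare. With equal true hazards, the apparent hazard ratio (T-Guard vs ruxolitinib) = 1 / (1 − h(1 − d)), because deaths cannot be hidden.

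| h | Hidden, 10% loss (3.2 events) | Hidden, 39% loss (12.5 events) | HR, d = 0 | HR, d = 0.5 |
|---|---|---|---|---|
| 10% | 0.3 | 1.2 | 1/0.90 = 1.11 | 1/0.95 = 1.05 |
| 20% | 0.6 | 2.5 | 1/0.80 = 1.25 | 1/0.90 = 1.11 |
| 30% | 1.0 | 3.7 | 1/0.70 = 1.43 | 1/0.85 = 1.18 |

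At the 10% loss reported for ruxolitinib, at most about 1 of 3 events is hidden. The hazard ratios are upper bounds for a given h and d: they treat a hidden flare as event-free for good, whereas a later death, steroid increase or added agent would still be counted, only later.

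**The case against.** The strongest reply is that the pathway is inferred. Nothing in the plan describes raising ruxolitinib for worsening aGVHD. A reader might take section 2.5.2.5 as permission to do so, but its re-escalation text covers recovery from a toxicity reduction only. That stands. Equally, nothing forbids it, and section 2.5.2.3 leaves tapering to judgment, so the event rule has to say how it is counted.

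A reader might also infer that a restart after a full stop is clearly not an event. The documents do not settle this. Section 2.5.3.1 says that resuming a GVHD prophylaxis agent is not adding a second agent; ruxolitinib has no such exemption, so a restart could be read as an initiation.

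A third reply is that this is a choice of estimand: response under the assigned ongoing strategy, dose adjustment included, is a defensible target, and raising or resuming a calcineurin inhibitor or mycophenolate is not listed as an escalation either. But those background agents are available in both arms, so that omission is symmetric. Only one study drug can be raised after Day 28. If the strategy reading is intended, the plan should say so and show the alternative.

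Finally, it might be inferred that GVHD-free survival carries the same bias in full. It does not. Success there requires being alive, stage 0 in all evaluable organs and free of cGVHD at Day 90 or 180 (sections 3.1 and 3.4.2.6). A participant in active flare fails in either arm. Only those back at stage 0 can be classified differently: after more ruxolitinib in one arm they can count as successes, while ruxolitinib begun in the other is additional systemic therapy and makes them failures.

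**Conclusion.** The point holds for dose increases: as written, the DoCR event rule depends on the arm, and the alternative definition shares the gap. For restarts the plan is ambiguous. The direction, against T-Guard, follows from the wording. The size is unknown, because the hidden share, the loss rate in this population and the share of deaths are all assumptions. The figures of 1.11 to 1.43 are ceilings under h of 10% to 30%, not expected distortions; with half the events deaths they fall to about 1.05 to 1.18.

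The stronger inference that the trial's error control is affected is not supported. DoCR carries no protected test, the primary endpoint is untouched, and a bias against T-Guard cannot manufacture a claim of longer response for it. What is at stake is a biased estimate of a key secondary endpoint. It is worth correcting because it is cheap now and may not be recoverable later: section 4.3.2 captures every corticosteroid dose change, but for immunosuppressants it names only overall start and stop dates, and no reason field for ruxolitinib changes is described.

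**What to change.** In sections 3.4.1.2 and 5.6.2, state that an increase or restart of ruxolitinib because of worsening aGVHD is a significant escalation for DoCR in both arms, and that a return to a higher dose after a toxicity reduction is not. At minimum, prespecify a DoCR sensitivity analysis that counts it. Add the matching sensitivity analysis for GVHD-free survival. Record the date and reason (toxicity recovery, taper, worsening aGVHD) of each ruxolitinib dose change through Day 180. The separate loss-of-CR definition in section 3.1, which also omits ruxolitinib changes, should be reconciled with the DoCR rule at the same time.

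The cost is one sentence in each section and one reason field. Ruxolitinib DoCR becomes slightly shorter. Sites must report dose changes made on commercial supply, which US participants use after Day 56 (section 2.5.2.2). The reason is assigned by the investigator in an open-label trial; the one-stage worsening condition limits that subjectivity in the primary DoCR definition but not in the alternative one. This concerns how events are counted and proposes no dosing rule.
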